## **Statistical Analysis**

The data will be analyzed using the IBM SPSS software package (Armonk, NY), with calculation of medians and standard errors. For continuous variables, the t-test and ANOVA will be used. For categorical variables, the Fisher's exact test will be used. A p value < 0.05 will be considered statistically significant.

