protective stoma, placement of drains, bowel preparation, role of the microbiome (17). Review from 2015 identified several patient-related modifiable and non-modifiable risk factors, including: male sex, smoking, habits, alcohol consumption, obesity, diabetes, vascular disease, use of anti-inflammatory drugs, transfusions, hypoalbuminemia, anemia, intraoperative hypotension and use of cardio-vascular drugs, neoadjuvant radiotherapy and chemotherapy(18).

A factor that occurs in almost all these conditions is an alteration in tissue perfusion, and therefore in oxygen availability with consequent micro-ischemia of affected segments and failure of the anastomosis.

Reduced availability of oxygen, in addition to the patient's condition, which can affect it both pre- and post-operatively, can also occur intraoperatively. Good tissue oxygenation can favorably influence the outcome of anastomoses. One study in fact has documented a reduction in the risk of AD following colorectal and gastric surgery with the administration of supplemental oxygen alone (FiO2 80%) during the procedure and for 6 hours thereafter (19).

However, the availability of O2 is not determined exclusively by the inspiratory fraction of O2, but by factors present in the equation that defines the Oxygen Availability (DO2):

$$DO_2 = CO \times CaO_2, \text{ where } CaO_2 = (Hb \times SaO_2 \times 1,39) + (0,0031 \times PaO_2)$$

CO: Cardiac Output; CaO2: Arterial Oxygen content

In this equation the portion of DO2 attributable to the dissolved form of O2 in arterial blood (PaO2) is negligible. Therefore the following equation can be considered:

$$DO_2 = CO \times Hb \times SaO_2 \times 1,39$$

Considering all the parameters involved allows to have a more correct and complete idea of peripheral tissue perfusion. There is only one study in literature in which the indexed DO2 (DO2I) is put in relation to the incidence of AD (20). In this study the CO of 75 patients undergoing colonic

resection was monitored via Doppler probe in the esophagus. The results show that patients with a DO2I <400 ml/min/m^2 have a significantly higher risk of developing AD.

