The use of the esophageal Doppler probe for monitoring cardiac dynamics is, however, highly invasive and cannot ignore the operator's experience. Furthermore, it requires frequent checks of the correct positioning of the probe itself. It also presents some, albeit rare, contraindications. Currently, there are several methods for cardiovascular monitoring that allow obtaining sufficiently reliable hemodynamic data while being less or absent invasive and easy to interpret. Through non-invasive analysis of the shape of peripheral blood waveform (pulse--contouring volume--clamp technique) by inflating a cuff placed on the patient's finger, it is possible to obtain complete information about volume status and preload, cardiac function and afterload, in an easily usable format (21--22).

To calculate DO2I it is also necessary to know the patient's total hemoglobin (Hb) value, data obtainable with a blood test, normally performed preoperatively. However, during the surgical intervention, numerous factors contribute to modifying the Hb concentration, such as the patient's volume status and blood loss.

To obtain reliable intraoperative data, it would therefore be necessary to resort to serial blood sampling, venous or arterial which is clearly invasive for the patient and an expenditure of economic resources. Currently, there are new-generation pulse oximeters on the market that analyze different wavelengths and simultaneously measure multiple parameters: O2 saturation, heart rate, respiratory rate, total hemoglobin, carboxyhemoglobin, and methemoglobin, arterial O2 content, perfusion index, and plethysmographic variability index.

With this new technology it is therefore possible to obtain non-invasively and continuously more real and complete data, little influenced by patient movement and by conditions of low perfusion (23--24).

Aim of the study

To evaluate the effects of DO2I on the incidence of AD in patients undergoing laparoscopic resection for colorectal cancer.

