## Materials and Methods

Patients attending the General Surgery Unit of the S. Eugenio Hospital in Rome will be enrolled who meet the following inclusion criteria:

- age > 18 years

- candidates for laparoscopic colorectal surgery in elective for neoplastic pathology

Patients will be excluded if they meet the following criteria:

- age < 18 years

- inability to express valid informed consent

- interventions that involve other areas of the body in addition to the colon and rectum

- emergency interventions

- open surgical interventions

- patients who have contraindications to the use of the volume--clamp system for hemodynamic monitoring (conditions that alter significantly the perfusion of the fingers, e.g. Raynaud's disease)

Each patient will follow a preoperative evaluation according to the clinical standards of the Anesthesia and Intensive Care Unit of the two recruiting centers: a complete physical examination will be conducted for all areas and a medical history aimed at identifying general and specific risk factors, and assigning a risk class of the American Society of Anesthesiologists (ASA).

During the preoperative period a blood sample will be taken for a complete blood count coagulation tests, and chemistry tests.

All patients will be given a dedicated informed consent form which will explain the aims and methods of the study. Furthermore, all patients will be informed that the anesthesiological care is of equal intensity in each case, in accordance with the dictates of common and good clinical practice.

Patients will be subjected to general anesthesia (GA) with titrated doses of propofol 1%, fentanyl, rocuronium, desflurane, oxygen, and air, with complete noninvasive monitoring.

All enrolled patients will also be provided with non-invasive hemodynamic monitoring for the calculation of CO based on pulse-contouring type volume clamp, via the ClearSight system (Edwards Lifescience Corporation--USA). Non-invasive monitoring will also be applied for oxygen calculation using pulse oximetry sensors Masimo rainbow (Masimo Corporation – Irvine, California). The DO2I will be calculated at three moments and periods during the procedure: 5 minutes after the induction of GA, 30 minutes after the induction of pneumoperitoneum, 5 minutes after the end of pneumoperitoneum. This is intended to record the variation in DO2I in relation to the hemodynamic changes induced by pneumoperitoneum.

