All patients enrolled will constitute Group A. Based on the average of three measurements of DO2I obtained during the intervention, patients in Group A will be distributed into three subgroups: DO2I <400 ml/min/m^2 (Group A1), DO2I 400--600 ml/min/m^2 (Group A2), DO2I >600 ml/min/m^2 (Group A3). The values of DO2I chosen as cut-offs for the formation of the three subgroups were established by analyzing the studies by Levy and by Shoemaker (20--25). For each of the three subgroups the incidence of AD will be calculated, also in relation to anamnestic risk factors.

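### Do the three DO2I readings need a stated within-patient analysis in the plan?

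*Combined protocol and SAP*

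**What the plan says.** Materials and Methods sets the DO2I readings at "5 minutes after the induction of GA, 30 minutes after the induction of pneumoperitoneum, 5 minutes after the end of pneumoperitoneum". It explains the schedule: "This is intended to record the variation in" DO2I "in relation to the hemodynamic changes induced by pneumoperitoneum". The same section then forms subgroups A1 to A3: "Based on the average of three measurements of" DO2I, each patient is placed below 400, at 400 to 600, or above 600 ml/min/m². AD incidence is calculated in each subgroup.

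The Statistical Analysis section describes the data "with calculation of medians and standard errors". It continues: "For continuous variables, the t-test and ANOVA will be used". Fisher's exact test is given for categorical variables, with significance at p < 0.05. No section defines a change score, a summary by time point, or the form of any comparison between time points.

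The single aim, at the end of the Introduction, is "To evaluate the effects of DO2I on the incidence of AD".

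**The concern.** The schedule exists to capture how DO2I moves with pneumoperitoneum, yet the one variable derived from it is an average, which removes that movement. The stated summaries do not bring it back. A standard error at one time point reflects the spread between patients and the sample size, whereas the precision of a within-patient change also depends on the correlation between readings. The usual standard error also belongs to a mean and not to the median it would sit beside.

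If the results were only medians and standard errors at each time point, a reader could not tell a clear change from one that might be chance. If the unspecified ANOVA were run as an independent-groups test on the three readings, it would be conservative and could miss a modest dip.

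**Working it through.** The plan gives no sample size, SD, correlation or expected change, so there is no figure of its own to reproduce. Correlation (rho), n and shift below are assumptions. The value n = 75 is the size of the earlier study described in the Introduction ("In this study the CO of 75 patients undergoing colonic" resection).

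**1. The average hides the course.** Hypothetical readings in ml/min/m²:

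| Readings | Average | Change, first to second |
|---|---|---|
| 450, 450, 450 | 1350/3 = 450 | 0 |
| 550, 350, 450 | 1350/3 = 450 | −200 |
| 350, 450, 550 | 1350/3 = 450 | +100 |

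All three patients fall in A2. The last column, however, comes from the recorded readings by subtraction. The average is a rule for forming subgroups and does not replace the readings.

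**2. Marginal standard errors do not give the precision of change.** With equal SDs, SE(change) = SE × √(2(1 − rho)). For a difference of 2 SE between two time-point **means**, z = 2/√(2(1 − rho)), and the 95% half-width is 1.96 × √(2(1 − rho)) SE.

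| rho | SE(change), in SE | z | Two-sided p | Half-width, in SE |
|---|---|---|---|---|
| 0.1 | 1.342 | 1.49 | 0.136 | 2.63 |
| 0.3 | 1.183 | 1.69 | 0.091 | 2.32 |
| 0.5 | 1.000 | 2.00 | 0.046 | 1.96 |
| 0.8 | 0.632 | 3.16 | 0.0016 | 1.24 |

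This holds for any n or SD, but only for means. A difference of medians is not the median change, and its standard error does not follow this formula. For normal data the SE of a median is about 1.25 times that of the mean.

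**3. What the wrong form of test would cost.** The simulation used compound symmetry, unit variance and a shifted middle reading, with n = 75. It compared ordinary ANOVA with repeated-measures ANOVA.

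| rho | Type I error, ordinary | Power at 0.3 SD, ordinary vs repeated |
|---|---|---|
| 0.1 | 3.7% | 44% vs 48% |
| 0.3 | 1.4% | 41% vs 60% |
| 0.8 | 0.0% | 27% vs 99% |

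Repeated-measures ANOVA keeps its type I error near 5%. For a 0.5 SD shift at n = 75 the loss is at most about 5.5 points, near rho 0.35 to 0.4. For 0.8 SD at n = 50 it is under 1 point. All of these losses depend on using the independent-groups form, which the plan does not specify.

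**4. What reaches the aim.** The AD comparison uses one average per patient, three subgroups and Fisher's exact test. No change score, time-point summary or time-point test enters it.

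**The case for a change.** The strongest case for amending is that recording variation is the only reason the protocol gives for the schedule, and it has no defined output. The contrast, the summary and the form of test are left open until the data are in hand. Step 2 shows that the stated descriptive measures alone cannot settle whether DO2I changed. Three sentences labelled secondary would close the gap without new measurements.

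Part of this stands. The text is silent, and a careful author would have named the paired form. But the ambiguity in step 2 needs a table with no test beside it, and the plan provides t-tests and ANOVA for continuous variables, of which DO2I is one. A paired or repeated-measures p-value would separate the two readings of the table. To record variation also promises less than to estimate or test it, and taking three timed readings does record it. The added wording would itself be a choice among acceptable options: a mixed model would serve as well as repeated-measures ANOVA and would not drop patients with a missing reading.

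The pairing of medians with standard errors is a fair criticism, but it is separate. It applies to every continuous variable and is corrected when the tables are prepared.

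**Conclusion.** No change to the plan is needed. This is missing detail that an analyst would fill sensibly: three readings on the same patient call for a paired or repeated-measures analysis, and the named tests include those forms. The descriptive ambiguity is real for time-point means (z from 1.49 to 3.16 for the same 2-SE difference as rho runs from 0.1 to 0.8, equal SDs assumed), but it arises only if no test or change is reported. The power losses are conditional on an error the plan does not make and rest on assumed n, correlation and shift. The AD analysis and the study's conclusion are unaffected. The judgement assumes that the three individual readings are kept alongside their average, as the schedule implies.
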